#### 1281 **4.6. Secondary Aim 2: Recurrence of HCC for deceased donor versus LDLT.**

1282 The utility of liver transplantation for patients with cirrhosis and hepatocellular 1283 carcinoma with stage 1 or 2 disease has clearly been demonstrated. The key to this 1284 therapy is timing of transplantation, and progression of disease while a patient is awaiting 1285 transplantation is a potential hazard. The near immediate availability of a graft from a 1286 living donor opens up the possibility of intervening with transplant before the 1287 complication of progression of disease is encountered. However, to date there has been 1288 no clear evidence that the benefits of this mode of therapy are superior to standard 1289 deceased donor transplantation as it relates to patient survival and cancer free survival. A 1290 prospective study to compare outcomes of these two treatment modalities is therefore 1291 needed.

1292

[figure not shown]
#### **4.6.1. Study Methods**

1294 This is a prospective cohort study which will collect data elements specific to a subset of 1295 patients enrolled in the A2ALL Cohort Study, who carry a diagnosis of cirrhosis and 1296 hepatocellular carcinoma. This cohort will include all LDLT recipients who consent to 1297 enrollment, have cirrhosis, and carry a diagnosis of hepatocellular carcinoma, or develop 1298 hepatocellular carcinoma while waiting for transplant. To address the Primary Aims and 1299 utilization of ablation, patients who undergo LDLT procedures (LDLT GROUP) will be 1300 compared with recipients who were enrolled but ultimately could not undergo a live 1301 donor transplant secondary to recipient or donor factors, and remained on the waiting list 1302 or eventually underwent deceased donor liver transplant (DDLT GROUP).

1303

1304 Since there will be a period of time before a suitable number of DDLT GROUP patients 1305 accumulate, a third group consisting of contemporaneous deceased donor controls will 1306 also be recruited (**CONTEMP GROUP**). These patients carry a diagnosis of cirrhosis 1307 and hepatocellular carcinoma, will be selected by the Data Coordinating Center, and 1308 enrolled at the time of transplant. This CONTEMP GROUP will serve as a control to 1309 address the question of operative and post-operative complication rates. It is anticipated that the CONTEMP GROUP will only be needed for the first two years of the study, 1310 1311 depending on number of patients enrolled.

- 1312
- 1313 A schematic for patient flow through the study is below.
- 1314

1315 1316 1317 1318 1319 1320	A2ALI	ents are enrolled in the study multiple data elements will be collected as part of the L Cohort Study. Specific data elements related to the subset of patients with cellular carcinoma, as well as their management while on the list is outlined below.
1321	1.	All enrolled patients with a confirmed or suspected diagnosis of HCC will first
1322		undergo evaluation to exclude metastatic disease and/or vascular invasion (chest
1323		CT, bone scan and abdominal MRI or contrast CT). These staging modalities and
1324		results will be recorded at 3-month intervals as required by UNOS.
1325	2.	All enrolled patients, who will wait > 3 months for transplant, will then undergo
1326		ablation of each lesion(s) with whatever technique(s) are currently utilized at each
1327		of the individual centers participating in this study (RFA, cryotherapy, alcohol
1328		ablation, chemoembolization, etc). The specific technique and all complications
1329		will be recorded.
1330	3.	Patients able to undergo LDLT (LDLT GROUP) will proceed with this procedure
1331		3 months following ablation or as soon thereafter as is possible.
1332	4.	Patients unable to undergo LDLT will be followed at periodic intervals and
1333		receive testing to assess for disease progression (chest CT, bone scan and
1334		abdominal MRI or contrast CT) every 3 months until they are able to undergo
1335		DDLT (DDLT GROUP).

1336	5. Patients with evidence of local recurrence of HCC during this waiting period may
1337	undergo repeat ablation in an attempt to limit disease progression prior to
1338	undergoing DDLT or LDLT.
1339	6. Patients who develop evidence of metastatic disease or vascular invasion will be
1340	dropped from the study protocol and followed until death.
1341	7. The liver explants of all patients who undergo LDLT or DDLT will be evaluated
1342	for presence of HCC under a defined pathologic protocol : EXPLANT
1343	PATHOLOGY:
1344	a. Explant liver will be sliced at 4-5mm intervals and all suspicious nodules
1345	for HCC processed for light microscopy.
1346	b. Tumors will be measured and inspected for encapsulation, invasion into
1347	adjacent liver, and vascular structures. Sections from the tumor/tumors
1348	will be fixed in formalin and processed for light microscopy. The size,
1349	multiplicity, grade (G1,G2,G3), degree of mitosis (<10/HPF or
1350	>/=10/HPF), infiltration into adjacent liver, encapsulation, and vascular
1351	invasion (micrometer vs. millimeter portal or hepatic vein ) will be
1352	determined for all tumors.
1353	8. All patients will be followed in the LDLT cohort main study protocol prior to and
1354	following LDLT and DDLT
1355	9. All patients who undergo LDLT or DDLT will be followed post transplant for
1356	evidence of recurrent or metastatic disease. Serum AFP will be determined at
1357	post-transplant month 3,6,12,18, 24 and every six months until the conclusion of
1358	the study. Patients will also undergo either an abdominal CT or MRI at months 6,
1359	12 and 24 post-transplant to document absence of recurrence. Criteria for disease
1360	recurrence include radiologic imaging demonstrating a lesion with characteristics
1361	of tumor (date and type of study to be recorded, possibilities include bone scan,
1362	PET scan, CT or MRI.) Tissue diagnosis is also acceptable but not required for
1363	diagnosis of recurrence. An elevated AFP in the absence of a documented lesion
1364	on imaging will not be accepted as evidence of recurrence.
1365	
1366	Primary endpoints will be patient survival, cancer-free patient survival.
1367	
1368	Secondary endpoints will include loss of candidacy while on list due to tumor
1369	progression, overall use of ablative therapies, complications of ablative therapies,
1370	accuracy of preoperative imaging modalities, surgical and postoperative complication
1371	rates.
1372	
1373	4.6.2. Participant Selection
1374	See Section 4. for overall eligibility criteria, and Section 4.2.2 for further details on
1375	selection of contemporaneous controls. The specific inclusion and exclusion criteria for
1376	patients with HCC are given below.
1377	
1378	Inclusion Criteria:
1379	
1200	

- 1. Suspected or confirmed HCC which meet the UNOS definition for being listed 1380 for Stage I or Stage II priority. 1381 1382
  - a. A single mass lesion on imaging studies < 5 cm in diameter

1383	b. Multiple lesions on imaging studies, but no greater than three lesions and
1384	no single lesion $> 3$ cm.
1385	c. A tissue diagnosis of HCC.
1386	d. An AFP greater than $> 500$ ng/ml.
1387	2. Patients with greater than Stage II disease will also be enrolled, as long as they
1388	were accepted by the individual transplant center as acceptable for liver
1389	transplant.
1390	3. Patients with history of ablation prior to listing will also be eligible, as long as
1391	one of the features in section 1 above was present prior to the ablative procedure.
1392	
1393	Exclusion criteria :
1394	
1395	1. Evidence of metastatic disease based upon chest CT, bone scan and abdominal
1396	MRI or contrast CT.
1397	2. No tumor found in explant and no history of prior ablative therapy.
1398	3. Patients with synchronous cholangiocarcinoma.
1399	
1400	4.6.3. Data Elements
1401	In addition to the data elements collected for the A2ALL Cohort study, specific data
1402	elements will be collected in these patients with HCC. These include:
1403	Detential Desiniants resitive for UCC
1404	Potential Recipients positive for HCC
1405	
 
HCC data at Listing
 
HCC data at Enrollment
 

1406 1407	2. HCC data at Enrollment
1407	Desirients positive for UCC
1408	Recipients positive for HCC 1. HCC Data Immediately Prior to Transplant
1409	
 
ACC Data Infinediately Flor to Transplant
 
ACC Explant Assessment
 

1410	
 
A HCC Explaint Assessment
 
HCC Post-operative Recurrence and Treatment Data
 

1411	5. Thee Post-operative Recurrence and Treatment Data
1412	
1413	4.6.4. Sample Size and Power Calculations
1414	It is anticipated (based on 1998-2002 data and trends) that approximately 75 patients
1415	(25% of all 300 LDLTs) will have undergone LDLT for HCC over the three-year period
1416	of the Retrospective study at the A2ALL study centers. Similarly, there should be
1417	approximately 125 patients (25% of all 500 non-LDLT) in the non-LDLT group to serve
1418	as controls. In addition, approximately 15% of Cohort patients are estimated to have
1419	HCC (0.15*360=) 54 LDLT and (0.15*710=) 106 non-LDLT. Thus, the total cohort for
1420	endpoints collected in both Retro and Cohort studies will be (75+54=) 129 LDLT and
1421	(125+106=) 231 non-LDLT. With this number of patients, there will be an 95% power to
1422	detect a 20% difference (e.g., 40% versus 60%) in recurrence of HCC (loss of transplant
1423	candidacy or post-transplant recurrence) between the LDLT group and non-LDLT group.

- 1424 These numbers should also allow for adequate comparison of patient survival, since
  - 1425 tumor recurrence typically leads to patient death.
  - 1426
  - 1427 The lowest power will be available for comparisons between LDLT and DDLT among
  - 1428Cohort patients only: an estimated 54 LDLT and 54 DDLT. For these comparisons,
Revised Cohort Protocol 031006Page 34 of 56

continuous outcomes will have more power than dichotomous outcomes. We will have 1429

1430 87% power to detect an effect size (number of standard deviations different) of 0.60

1431 between groups. Cohen considers and effect size of 0.50 to be moderate, and 0.90 to be 1432 large.

1433

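### Exclusion 2 of the HCC study removes unablated patients with tumor-free explants, so patient-level imaging accuracy in unablated recipients cannot register a false positive

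*Protocol*

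**What the plan says.** Four parts of the HCC section (Secondary Aim 2) bear on this.

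- **Endpoint.** The secondary endpoints at the end of Protocol 4.6.1 include "accuracy of preoperative imaging modalities, surgical and postoperative complication" rates.
- **Entry.** Inclusion criterion 1 in 4.6.2 starts from "Suspected or confirmed HCC which meet the UNOS definition for being listed" at Stage I or II priority. It then lists four features, the first being "A single mass lesion on imaging studies < 5 cm in diameter". The others are a limited number of small lesions, a tissue diagnosis, and an AFP above 500 ng/ml. Criterion 3 speaks of one of these features being present, so they read as alternatives and an imaging lesion can suffice.
- **Reference standard.** Item 7 of 4.6.1: "The liver explants of all patients who undergo LDLT or DDLT will be evaluated" for HCC under a set pathology protocol.
- **Exclusion.** Exclusion criterion 2 in 4.6.2: "No tumor found in explant and no history of prior ablative therapy".

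Ablation is tied to waiting time in item 2 of 4.6.1: "All enrolled patients, who will wait > 3 months for transplant, will then undergo" ablation of each lesion. Nothing in the protocol exempts the imaging endpoint from exclusion 2 or gives it a population of its own.

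**The concern.** The accuracy of a scan is judged by comparing it with what the pathologist finds. Here the study population is defined partly by the pathologist's finding. A patient who enters on a suspicious lesion, is never ablated, and proves to have no tumor is the diagnostic error that an accuracy endpoint exists to count. Exclusion 2 takes that patient out of the HCC study before the count is made.

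The exclusion makes sense for recurrence, since a patient without HCC cannot have it recur. Applied to imaging accuracy, it conditions the analysis set on the reference standard. At stake is whether the reported accuracy in unablated recipients reflects how the scans performed or only how the patients were selected.

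**Working it through.** The protocol gives no figure for imaging accuracy, so there is none to reproduce. The point is mainly a matter of logic, with an illustration of size.

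**1. Two-by-two table for transplanted, unablated patients**

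| | Tumor in explant | No tumor in explant |
|---|---|---|
| Scan positive | TP, kept | FP, removed by exclusion 2 |
| Scan negative (entered on AFP, for example) | FN, kept | TN, removed by exclusion 2 |

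- PPV = TP / (TP + FP) = TP / (TP + 0) = 100%, whatever the true false-positive share.
- Specificity = TN / (TN + FP) = 0 / 0, which cannot be estimated.
- Overstaging: a patient staged I or II on imaging with no tumor at all is its extreme form. Removing these patients lowers the observed overstaging rate.

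**2. Ablated and unablated patients pooled**

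Consider scan-positive transplanted patients. Let *a* be the ablated share, *f* the true false-positive share, and *c* the share of ablated true positives whose tumor is completely destroyed. None of these is in the protocol; the values below are assumptions. Ablated patients stay in whatever the explant shows.

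Apparent PPV = [(1 − a)(1 − f) + a(1 − f)(1 − c)] / [(1 − a)(1 − f) + a]

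With a = 0.5 and f = 0.10, so a true PPV of 90%:

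- c = 0: (0.45 + 0.45) / (0.45 + 0.50) = 0.90 / 0.95 = 94.7%
- c = 0.20: (0.45 + 0.36) / 0.95 = 0.81 / 0.95 = 85.3%

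The pooled figure is not fixed at 100% and can err in either direction. In ablated patients a clean explant may mean a false-positive scan or a successful ablation, and the explant alone cannot separate the two.

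**3. How many patients are removed**

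Section 4.6.4 expects 54 LDLT and 54 DDLT recipients with HCC in the Cohort Study: 54 + 54 = 108. Assume 20 to 50% are unablated and 10 to 20% of those have a tumor-free explant.

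- Low end: 108 × 0.20 × 0.10 = 2.2, about 2 patients
- High end: 108 × 0.50 × 0.20 = 10.8, about 11 patients

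Among those removed, the scan-positive ones are lost false positives and any scan-negative ones are lost true negatives.

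**The case against.** The strongest reply is that the protocol never mentions predictive value. Item 1 of 4.6.1 treats the scans as staging tools, item 7 records tumor size, number and vascular invasion, and 4.6.5 describes patients by explant stage. Accuracy may therefore mean lesion-level or staging agreement, which survives in the retained patients: extra lesions, missed lesions and wrong stage all remain visible. This stands. A reader might infer that the endpoint can show no diagnostic error at all, or that PPV is 100% for the whole HCC cohort. The documents support neither, since ablated patients with clean explants are kept.

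A second reply is that few patients are unablated. Item 2 of 4.6.1 has patients with waits beyond three months ablated, and item 3 describes LDLT as following ablation. An unablated share of one half fits poorly with those items, which is why it is only the upper end of the range above.

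Third, the choice of metric can be left to a statistical analysis plan, which is not at hand. That is right, and the undefined metric is not the complaint. The complaint is that an exclusion already written into the protocol biases a named endpoint, and a later plan using the HCC population as written would inherit that bias.

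Finally, the information is not lost. Explants are read in all transplanted patients, and item 8 keeps all patients in main-study follow-up. This also stands, and it makes the repair cheap.

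**Conclusion.** The point holds in a limited form. Among transplanted, unablated patients, exclusion 2 fixes patient-level PPV at 100%, leaves specificity without a denominator, and understates overstaging. These results follow from the criteria as written and need no numerical assumption, only that the explant serves as the reference standard.

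The size does rest on assumptions. About 2 to 11 of 108 recipients are removed if 20 to 50% are unablated and 10 to 20% of those are tumor-free. Lesion-level and staging agreement remain estimable in the retained patients, and pooled PPV is distorted but not fixed.

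Severity is minor. Imaging accuracy is one item in a secondary-endpoint list of a secondary aim. It does not appear in the HCC objectives in section 3.6, in the power section 4.6.4 or in the analyses in 4.6.5. A reader might also infer that the result would guide who is transplanted on imaging alone; the protocol does not say so.

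**What to change.** State in 4.6.2 that exclusion 2 does not apply to the imaging-accuracy analysis, and define that analysis as follows:

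- **Population:** all transplanted patients enrolled with suspected or confirmed HCC who have both a pre-transplant scan and an explant reading.
- **Counting:** scan positive with a tumor-free explant is a false positive; scan negative with a tumor-free explant is a true negative. The second rule is needed because patients can enter on AFP or a tissue diagnosis.
- **Reporting:** ablated and unablated patients separately, because ablation changes what the explant shows.

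Leave exclusion 2 unchanged for every other HCC endpoint, including survival, recurrence and complications. Lifting it there would change the populations of comparisons that this point does not touch.

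The cost is a few lines of text. The scans and explant readings are already collected, and no procedure changes. The reported accuracy is likely to look slightly less favourable.

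### The explant-based exclusion for HCC in 4.6.2 can reach only transplanted patients, so it removes tumor-free suspected cases unequally from the LDLT versus non-LDLT comparison; size and direction depend on who was ablated

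*Protocol*

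**What the plan says.** **Entry.** Protocol 4.6.2 admits "Suspected or confirmed HCC which meet the UNOS definition for being listed" for Stage I or II priority, and also more advanced disease if the center accepts the patient. Proof of tumor is not needed.

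**Exclusion.** The second exclusion criterion in 4.6.2 is "No tumor found in explant and no history of prior ablative therapy".

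**Who has an explant.** Step 7 of 4.6.1: "The liver explants of all patients who undergo LDLT or DDLT will be evaluated". Nobody else can have one.

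**Comparison groups.** For the main objectives of this aim, 4.6.1 sets LDLT recipients against enrolled patients who could not have a live "donor transplant secondary to recipient or donor factors, and remained on the waiting list" "or eventually underwent deceased donor liver transplant (DDLT GROUP"). The table of study populations in Section 4 fixes this HCC comparison at the donor history and physical. It lists the at-transplant LDLT versus DDLT comparison on a separate line.

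**Endpoint used for power.** Section 4.6.4 counts recurrence as loss of transplant "candidacy or post-transplant recurrence) between the LDLT group and non-LDLT group".

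**Ablation.** Step 2 of 4.6.1: "All enrolled patients, who will wait > 3 months for transplant, will then undergo" ablation. Step 3: "Patients able to undergo LDLT (LDLT GROUP) will proceed with this procedure" three months after ablation, or as soon as possible after that.

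Nothing in 4.6 limits the explant rule to the at-transplant comparison, and no equivalent rule covers patients who are never transplanted.

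**The concern.** The comparison begins at donor evaluation, but the exclusion rests on a finding that appears later and only if the patient is transplanted. Transplantation by LDLT is the exposure being compared. A suspected case without tumor who receives LDLT unablated is removed. The same kind of patient who stays on the list, leaves it or dies waiting remains in the control group.

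Patients with no tumor have little or no risk of HCC recurrence or of losing candidacy through tumor progression. Removing more of them from one group than from the other shifts that group's event proportion without any effect of treatment. The analyses affected are the LDLT versus non-LDLT difference in recurrence proportions and the Cox comparison of survival, both in 4.6.5. These serve the primary objectives and endpoints within Secondary Aim 2, not a primary aim of the study.

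**Working it through.** **Plan's own figure.** Section 4.6.4 gives 95% power for 40% versus 60% with 129 LDLT (75 + 54) and 231 non-LDLT (125 + 106). A two-sided 0.05 test of two proportions gives 95.7% (94.6% with continuity correction). The level is not stated in 4.6.4 and is taken from the other power sections. The figure is sound.

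**Model for the exclusion.**
- f: share of enrolled HCC patients who have no tumor, equal in both groups. Assumption; the protocol gives no rate.
- r: event risk in true HCC. Assumption; 40% is one of the values in 4.6.4.
- e: event risk in tumor-free patients. Assumption: 0.
- t: share of controls transplanted. Assumption: 0.5. This agrees with 355 DDLT (4.5.4) of 710 non-LDLT (4.1.4) and 54 of 106 in 4.6.4, although those DDLT counts may include contemporaneous controls.
- aL, aN: share ablated before transplant among LDLT patients and among transplanted controls. Assumption.

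Share of tumor-free patients removed: dL = 1 − aL in LDLT, and dN = t(1 − aN) in controls.

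Observed risk = [r(1 − f) + e·f(1 − d)] / [(1 − f) + f(1 − d)].

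**No ablation in either group** (dL = 1, dN = 0.5), e = 0. The observed LDLT risk is r and the control risk is r(1 − f)/(1 − 0.5f).

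| r | f | LDLT | Control | Spurious excess in LDLT |
|---|---|---|---|---|
| 40% | 5% | 40.0% | 0.38/0.975 = 39.0% | 1.0 points |
| 40% | 10% | 40.0% | 0.36/0.95 = 37.9% | 2.1 points |
| 40% | 20% | 40.0% | 0.32/0.90 = 35.6% | 4.4 points |
| 60% | 20% | 60.0% | 0.48/0.90 = 53.3% | 6.7 points |

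At f = 10% the rule removes about 13 of 129 LDLT patients (10%) and about 12 of 231 controls (5%).

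**Effect of ablation.**
- 70% ablated in both transplanted groups, r = 40%, f = 10%: LDLT 0.36/0.97 = 37.1%, control 0.36/0.985 = 36.5%. The excess falls from 2.1 to 0.6 points.
- 70% of transplanted controls ablated and no LDLT patients, r = 50%, f = 10%: excess 4.3 points, against 2.6 with no ablation at the same r.
- All transplanted patients ablated: dL = dN = 0, excess 0.
- 70% of LDLT ablated, 80% of controls transplanted and 40% of those ablated, r = 50%: −0.4 points at f = 5% to −2.4 at f = 30%.

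**Sign.** The excess is positive when 1 − aL > t(1 − aN). With t below 1 this holds whenever aL is no larger than aN and some LDLT patients are unablated. It reverses when aL > 1 − t(1 − aN). At t = 0.5 and aN = 0.4, that means aL above 70%.

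**If tumor-free patients also have events** (e = 20%, r = 50%, no ablation): 0.8, 1.6 and 3.3 points at f = 5, 10 and 20%.

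**Effect on the planned contrast.** Take 40% versus 60% as the whole-group risks before exclusion, with no ablation and e = 0. At f = 10% the analysed risks are 0.40/0.90 = 44.4% and 0.60/0.95 = 63.2%, a gap of 18.7 points (power 91%). At f = 20% they are 50.0% and 66.7%, a gap of 16.7 points (power 81%).

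**The case against.** The strongest counter is step 3 of 4.6.1. Read literally, LDLT follows ablation, and ablation exempts a patient from the exclusion, so few prospective LDLT patients would be removed. This stands as a limit on size and direction. It does not settle the matter, because step 2 ties ablation to an expected wait of more than three months, and the two steps do not say whether an LDLT patient with a shorter expected wait is ablated.

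Second, the tumor-free share may be low. The general HCC criteria in Section 4 ask for a diagnosis, and 4.6.1 describes patients who carry one. That argues against the upper end of the range, but 4.6.2 still admits suspected cases.

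Third, 1 to 2 points is small beside the 20-point target, or beside a 95% interval half-width of about 10.6 points (1.96 × √(0.24/129 + 0.24/231)). True, but the shift is systematic and avoidable.

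Fourth, tumor-free patients are not wholly free of events: 4.6.1 includes patients who develop HCC while waiting, and recurrence may be called on imaging alone. This reduces the bias without removing it, as the e = 20% case shows.

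A reader might infer that the rule makes LDLT look worse in every case, on survival as well as recurrence. The documents do not support that. The sign depends on ablation patterns that the protocol leaves open. Tumor-free patients left waiting still have cirrhosis and can die of it, and no calculation here covers survival.

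**Conclusion.** The structural fault holds. Exclusion 2 selects on a post-entry finding tied to the exposure, and nothing confines it to the comparison in which both groups have explants.

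If ablation before transplant is no more common in LDLT patients than in transplanted controls, recurrence or loss of candidacy in the LDLT group is spuriously raised. The size is about 1 to 4 points, given no ablation, 40% risk, half the controls explanted and 5 to 20% tumor-free, none of which the protocol establishes. The bias shrinks with common ablation in both groups, is zero if all transplanted patients were ablated first, and can reverse if LDLT patients are ablated clearly more often. The direction for overall survival is not established. The stated 95% power is not in error.

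**What to change.** 1. In 4.6.2, define the HCC population for the LDLT versus non-LDLT comparison only on data known at donor evaluation, and keep those patients whatever the explant shows.
2. Restrict exclusion 2 to the at-transplant LDLT versus DDLT recurrence comparison. Report a sensitivity analysis there without it, because the ablation exemption may still be unequal between those two groups.
3. Reconcile steps 2 and 3 of 4.6.1 on ablation and the timing of LDLT, so that it is clear who falls under the exemption. Which clinical sequence applies is for the investigators.

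The cost is wording only. No new data are needed, since step 8 of 4.6.1 keeps all patients in the main protocol's follow-up. The planned 129 versus 231 and the 95.7% power are retained. The downside is slight dilution of recurrence by patients without HCC.
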